1.0 Background

1.1 Disease Background

Hodgkin lymphoma (HL) is predicted to affect over 9,000 patients in the United States in 2015, approximately 20% of which are greater than 60 years old¹. While current front-line regimens such as adriamycin, bleomycin, vinblastine and dacarbazine (ABVD) and Stanford V produce long-term remissions in younger patients (5-year overall survival (OS) 90%)², their efficacy is less in the elderly. In E2496, a phase III study of 45 patients 60 years or greater, ABVD and Stanford V regimens produced an overall response rate (ORR) of 68%, a complete response (CR) rate of 64%, and a 5-year OS of only 58%³. Furthermore, treatment related mortality (TRM) was 9% with increased rates of grade 3-4 neutropenia (82%) and anemia (24%) and grade 3-5 infections (11%) and pulmonary toxicity (24%). The age-related disparity in overall survival with a potentially curable lymphoma demonstrates the need for alternative, more tolerable, front line options for the elderly.

New biologic molecules have been developed recently to specifically target the malignant lymphocyte and its microenvironment with a goal of improving anti-tumor efficacy, while limiting toxicity. Brentuximab vedotin (BV) is an antibody drug conjugate (ADC) comprised of a chimeric anti-CD30 monoclonal antibody joined to a microtubule-disrupting agent, monomethyl auristatin E (MMAE), via a citrulline valine linker. BV gained its approval based on a phase II study demonstrating an ORR of 75% (CR 34%), median progression free survival (PFS) of 9.3 months, and a 3-year OS of 40.5 months in patients with relapsed and refractory HL following autologous transplant^{4,5}. In a single-agent front-line phase II study of HL patients > 60 years-old treated with BV, the interim analysis of 27 patients reported an ORR 93%, a CR rate of 70% and PFS of 8.7 months. The drug was well tolerated with reports of > grade 3 adverse effects of neutropenia (22%), peripheral sensory and motor neuropathy (7% each) and rash (7%)⁶. It is currently under study in the ECHELON trial in combination with Adriamycin, vinblastine and dacarbazine, being compared with traditional ABVD.

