- 1.228 A total of 9 deaths were reported within the safety evaluation period (within 30 days of the last dose of brentuximab vedotin) in 357 patients across the 6 phase 1 and phase 2 studies for which data are available. Two patient deaths (0.6%) were considered related to study treatment. One patient in Study SG035-0001 who received 3.6 mg/kg in phase 1 died due to febrile neutropenia and presumed septic shock. A second treatment-related death in Study SGN35-008A was attributed to pancytopenia, cytomegalovirus (CMV) infection, and intracranial hemorrhage. The remaining on-study deaths were primarily related to disease progression in sALCL patients.
- 1.229a Brentuximab vedotin has been shown to induce durable remissions in patients with HL both pre- and post-ASCT, and in patients with relapsed or refractory sALCL. PFS results comparing PFS with brentuximab vedotin to PFS from prior systemic therapy indicate that PFS is significantly prolonged with brentuximab vedotin for both HL and sALCL. A substantial number of HL and sALCL patients with B symptoms at baseline saw these symptoms resolve during treatment with brentuximab vedotin. In addition, the large majority of sALCL patients presenting with cutaneous lesions at baseline experienced resolution of these symptoms after receiving brentuximab vedotin. Study SGN35-009 is a phase 1, 2-arm, open label, multicenter study to evaluate the safety of brentuximab vedotin when administered in combination with standard therapy (ABVD) or a modified standard

(doxorubicin (Adriamycin), vinblastine, dacarbazine [AVD]). To date, patients have received doses of 0.6, 0.9, or 1.2 mg/kg brentuximab vedotin with standard doses of ABVD or 1.2 mg/kg brentuximab vedotin with AVD, depending upon cohort assignment. The combination regimens are administered on Days 1 and 15 of each 28-day cycle for up to 6 cycles of therapy. Each regimen evaluated a dose limiting toxicity (DLT) period, defined as any Cycle 1 toxicity requiring a delay of ≥ 7 days in standard ABVD or AVD therapy. No DLTs were observed. Enrollment of an expansion cohort further testing 1.2 mg/kg brentuximab vedotin plus AVD is now complete and treatment of enrolled patients is ongoing within this cohort.

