The largest success proportion where the proposed treatment regimen would be considered ineffective in this population is 65%, and the smallest success proportion that would warrant subsequent studies with the proposed regimen in this patient population is 80%. The following one-stage design with an interim analysis is based on a two-stage Simon optimum design and requires 56 evaluable patients to test the null hypothesis that the true success proportion in this patient population is at most 65%.

16.211 Interim Analysis: Enter 25 evaluable patients into the study. If 17 or fewer successes are observed in the first 25 evaluable patients, we will consider this regimen ineffective in this patient population and terminate the study. Otherwise, if the number of successes is at least 18, we will continue accrual.

16.212 Final Decision Rule: Enter an additional 31 evaluable patients into the study. If 40 or fewer successes are observed in the first 56 evaluable patients, we will consider this regimen ineffective in this patient population and terminate this study. Otherwise, if the number of successes is at least 41, this will be considered evidence of promising activity and the treatment may be recommended for further testing in subsequent studies in this population.

16.213 Over Accrual: If more than the target number of patients are accrued, the additional patients will not be used to evaluate the stopping rule or used in any decision making process. Analyses involving over accrued patients are discussed in Section 16.313.

16.214 NOTE: We will not suspend accrual at the interim analysis to allow the first 25 patients to become evaluable, unless undue toxicity is observed. Given the limited

overall sample size and the inclusion of an adverse events stopping rule, we feel it is ethical to not halt accrual for the interim analysis. However, if accrual is extremely rapid, we may temporarily suspend accrual in order to obtain safety data on these patients before re-opening accrual to further patients.

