- 16.51 The principal investigator(s) and the study statistician will review the study at least twice a year to identify accrual, adverse event, and any endpoint problems that might be developing. The Mayo Clinic Cancer Center (MCCC) Data Safety Monitoring Board (DSMB) is responsible for reviewing accrual and safety data for this trial at least twice a year, based on reports provided by the MCCC Statistical Office.
- 16.52 Adverse Event Stopping Rules (to include all patients treated at the dose level determined in the early safety analysis): The stopping rules specified below are based on the knowledge available at study development. We note that the Adverse Event Stopping Rule may be adjusted in the event of either (1) the study re-opening to accrual or (2) at any time during the conduct of the trial and in consideration of newly acquired information regarding the adverse event profile of the treatment(s) under investigation. The study team may choose to suspend accrual because of unexpected adverse event profiles that have not crossed the specified rule below. Accrual will be temporarily suspended to this study if at any time we observe events considered at least possibly related to study treatment (i.e. an adverse event with attribute specified as "possible," "probable," or "definite") that satisfy one of the following:
- if 5 or more patients in the first 15 treated patients experience a grade 4 or higher non-hematologic adverse event at least possibly related to treatment.

- if after the first 15 patients have been treated, 30% of all patients experience a grade 4 or higher non-hematologic adverse event at least possibly related to treatment.

We note that we will review grade 4 and 5 adverse events deemed “unrelated” or “unlikely to be related”, to verify their attribution and to monitor the emergence of a previously unrecognized treatment-related adverse event.

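### After the six-patient lead-in, no numeric safety rule is specific to treatment-related death, and a related death coded only to a hematologic term does not count under Section 16.52

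*Combined protocol and SAP*

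**What the plan says.** All of the documents are in the combined protocol and SAP.

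- **The rule (16.52).** "Accrual will be temporarily suspended to this study if at any time we observe events considered at least possibly related to study treatment" and that meet one of two criteria. The first applies "if 5 or more patients in the first 15 treated patients experience a grade 4 or higher non-hematologic adverse event". The second applies "if after the first 15 patients have been treated, 30% of all patients experience a grade 4 or higher non-hematologic adverse event". Both need at least possible attribution to treatment. The population is "to include all patients treated at the dose level determined in the early safety analysis".
- **Discretion (16.52).** "The study team may choose to suspend accrual because of unexpected adverse event profiles that have not crossed the specified rule below". No number is attached.
- **Lead-in (7.12, 16.4).** Accrual is halted while each cohort of six is observed for one cycle. Related toxicity of Grade 4 or higher counts as a DLT, hematologic toxicity included, with listed exceptions. Two or more DLTs in six lead to a change of dose level, or to temporary closure at level -2.
- **Oversight.** The DSMB and the investigators each review the study at least twice a year (16.51). The investigators hold a weekly call (7.1). Deaths within 30 days of the last dose are reported within 24 hours (10.331). None of these carries a numeric trigger for accrual.
- **Weight placed on the rule (16.214).** Accrual is not paused at the interim analysis. Two reasons are given: the limited sample size and "the inclusion of an adverse events stopping rule, we feel it is ethical to not halt accrual for the interim analysis".
- **Benchmark (1.1).** Treatment-related mortality on chemotherapy was 9% in a study of 45 patients aged 60 or over.

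**The concern.** A rule that pools Grade 4 and Grade 5 events at roughly a 30% threshold is set for severe toxicity in general. A tolerable rate of related death is far lower than a tolerable rate of Grade 4 toxicity, so a pooled threshold says little about mortality. Section 1.1 uses the 9% chemotherapy figure to argue for a more tolerable option, yet no limit in the plan is tied to that figure.

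The rule also leaves out hematologic events at every grade, and 16.52 does not define which terms are hematologic. A related Grade 5 event with only a hematologic code would not count.

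What is at stake is accrual in older or less fit patients, on a combination that Section 7.1 says had not been studied before. Response is read at the end of cycle 8, about 27 to 29 weeks after start (7 × 3 = 21 weeks, plus 6 to 8). At 25 to 30 patients a year (16.23), about 13 to 17 more patients enter while patient 25 matures (25 × 27/52 = 13.0; 30 × 29/52 = 16.7). Between six-monthly reviews, 12 to 15 may enter. Section 16.52 is the numeric protection over those periods.

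**Working it through.** **Plan's own figures.** Section 16.52 states no operating characteristics, so there is none to reproduce there. The efficacy table in 16.24 was reproduced as a check on the method. Power = Σ over x = 18 to 25 of b(25, x, p) × P(Bin(31, p) ≥ 41 − x). The interim stopping probability is P(Bin(25, p) ≤ 17).

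| True p | Power, computed (stated) | Interim stop, computed (stated) |
|---|---|---|
| 0.65 | 0.097 (0.10) | 0.694 (0.69) |
| 0.70 | 0.293 (0.29) | 0.488 (0.49) |
| 0.75 | 0.593 (0.59) | 0.273 (0.27) |
| 0.80 | 0.852 (0.85) | 0.109 (0.11) |

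The table is right.

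**Step 1: what the rule tolerates.** The inputs are 5 of 15 and 30% (16.52), and a maximum of 56 evaluable patients (16.22).
- First 15 patients: 5/15 = 33.3% triggers and 4/15 = 26.7% does not. The exact 95% interval for 4/15 is 7.8% to 55.1%.
- After 15, the trigger is the smallest k with k/n ≥ 0.30. At n = 25, 0.30 × 25 = 7.5, so k = 8. At n = 56, 0.30 × 56 = 16.8, so k = 17.
- Therefore 16/56 = 28.6% does not trigger.

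**Step 2: chance of triggering if deaths are the only qualifying events.** Let p be the true rate of related deaths that carry a non-hematologic code. An exact recursion adds one patient at a time and removes the probability of any path that reaches the limit (5 for n ≤ 15, then k as above).

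| True death rate | By n = 15 | By n = 56 |
|---|---|---|
| 9% | 0.008 | 0.014 |
| 15% | 0.062 | 0.111 |
| 20% | 0.164 | 0.303 |
| 30% | 0.485 | 0.798 |

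The 9% rate is the protocol's own figure (0.09 × 45 ≈ 4 deaths). The others are assumptions.

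**Step 3: effect of pooling.** Grade 4 events also count, so Step 2 is a lower bound. If 9% of patients die and a further 15% to 21% (assumed) have a related non-hematologic Grade 4 event, the combined rate is 24% to 30%. The same recursion then gives 0.51 to 0.80 by n = 56.

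**Step 4: the lead-in.** If p is the rate of cycle-1 DLT, P(2 or more of 6) = 1 − (1 − p)^6 − 6p(1 − p)^5. This is 0.10 at 9%, 0.34 at 20% and 0.58 at 30%. It covers cycle 1 in cohorts of six, while treatment runs to 8 cycles. Four related deaths in 15 patients pass both formal rules only if at most one of the first six patients has a cycle-1 DLT.

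**Step 5: an illustrative death limit.** Suspend for review at 3 related deaths within the first 25 patients, or at 5 by 56. Same recursion:

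| True related mortality | 2% | 3% | 4% | 5% | 6% | 7% | 9% | 15% |
|---|---|---|---|---|---|---|---|---|
| P(trigger by 56) | 1.6% | 5% | 12% | 20% | 31% | 42% | 63% | 95% |

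**The case against.** The strongest reply is that the plan has more protection than 16.52 alone, and that 16.52 detects more than Step 2 suggests.

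- **Other safeguards.** The lead-in is a formal rule, counts hematologic toxicity and halts accrual. DSMB review and 24-hour death reports are mandatory; only the action that follows is left to judgement. Sections 16.214 and 16.22 make an exception for undue toxicity, and 16.25 lets adverse events bear on termination. None of these is limited to non-hematologic events. This stands. A reader might infer that four deaths in 15, or any number of hematologic deaths, would leave accrual open. The documents do not support that. They show only that 16.52 would not require suspension.
- **Pooling.** A regimen that kills patients will probably also cause Grade 4 events, and Step 3 shows how much this helps. It would be wrong to say that the rule cannot detect high mortality. But that detection depends on a Grade 4 rate that the plan does not state.
- **The deaths in Section 1.228.** A reader might cite these two brentuximab vedotin deaths as examples that 16.52 would miss. They are not. One involved presumed septic shock and was at 3.6 mg/kg, twice this trial's 1.8 mg/kg starting dose. The other is described thus: "A second treatment-related death in Study SGN35-008A was attributed to pancytopenia, cytomegalovirus (CMV) infection, and intracranial hemorrhage". Each has a non-hematologic component that could count.
- **Section 16.214.** The stopping rule is one of two reasons given for not pausing, not the only one.
- **False pauses.** The illustrative limit pauses accrual 12% to 42% of the time at 4% to 7% mortality, all better than the 9% benchmark, and triggers only 63% of the time at 9%. This stands, and it is why the cutoffs should not be taken from here.

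**Conclusion.** The point holds as a cheap improvement to the design. It is not an error or a contradiction in the plan. After the lead-in, no numeric limit is specific to related death, and a related death with only a hematologic code does not count. Below the 16.52 threshold, suspension depends on discretion, the weekly call and review at least twice a year.

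The size is a trigger probability of 1.4%, 11% and 30% by 56 patients at true death rates of 9%, 15% and 20%. These figures assume that deaths are the only qualifying events, that all have a non-hematologic code, that patients are independent, that 30% means at least 30%, and that the count is checked after every patient with outcomes known at once. The first assumption makes them a lower bound. The 9% benchmark rests on 45 patients and is itself imprecise.

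**What to change.** In Section 16.52:

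1. Count every at least possibly related Grade 5 event, whether its code is hematologic or not.
2. Add a separate limit on related deaths that suspends accrual temporarily for review. The sponsor and DSMB should choose the cutoffs. State the trigger probabilities over a range of true mortality on both sides of 9%, as 16.24 does for efficacy. The limit in Step 5 is an illustration of the format and not a recommendation.
3. Keep the existing Grade 4 rule unchanged.

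The cost is a few lines of text, and 16.52 already allows the rule to be adjusted during the trial. The downside is some chance of a temporary accrual pause when true related mortality is below 9%. For the illustrative limit that chance runs from 1.6% at 2% mortality to 42% at 7%, and it should be disclosed with whatever limit is chosen.

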17.1 Tissue Biospecimen Submission

17.11 Summary Table of Tissue Biospecimens for This Protocol

Type of tissue biospecimen to submit	Mandatory or optional	When to submit	Reason for submission (background/methodology section)	Where to find specific details for biospecimen submission
Formalin-fixed paraffin-embedded (FFPE) tissue blocks with corresponding H&E (OR (10) 5 micron unstained slides with corresponding H&E)**	Mandatory	Within ≤14 days following registration	Correlative biomarkers, tumor genetic variability and Banking	Section 17.31

17.2 Paraffin Embedded Tissue Blocks/Slides

17.3 Submit one formalin fixed paraffin-embedded (FFPE) tissue block Biopsy material obtained at the time of recurrence is preferred, but if not available, biopsy material obtained at the time of initial diagnosis of Hodgkin Lymphoma may be submitted *OR* Please submit biopsy material from each surgery.) **A corresponding H&E slide for each submitted block must be provided** to permit quality assessment of each tissue block.

17.31 The FFPE tissue block is preferred; however, **if an institution is unable to provide a tissue block**, cut (11) 5 micron unstained slides and mount on charged glass slides. **Label the slides with ACCRU patient ID number, accession number, and order of sections.** H&E stain the first slide (i.e., slides labeled 1, 11, etc.). These H&E slides will be reviewed centrally under the research base’s protocol for assessing tissue quality. **Do not bake or place covers slips on the slides.**

17.32 The following materials below are mandatory and required for shipment:

- Paraffin embedded tissue blocks with corresponding H&E slide (OR (10) 5 micron unstained slides with corresponding H&E(s)).

17.33 [Redacted] to notify Mayo Clinic Reference Laboratory when the specimen(s) are being shipped.

17.34 Specimens should be shipped to the following address:

[Redacted]
[Redacted]
[Redacted]
[Redacted]
[Redacted]

17.4 Tumor Assays

17.41 **Immunohistochemistry (IHC):** Previous studies of tumor biomarkers have shown that the tumor microenvironment in Hodgkin lymphoma is very important. These studies have shown that the number, phenotype and distribution of intratumoral immune cells predicts response to therapy. To confirm the prognostic or predictive role of immune cells in patients with Hodgkin lymphoma treated with brentuximab vedotin and nivolumab, we will use submitted paraffin-embedded tissue to measure the T-cell and macrophage infiltrate and correlate cell numbers and location with patient response and progression – free survival. As described above, serial 5- μ m paraffin-embedded sections will be used for IHC. The tissue will be deparaffinized with three changes of xylene and cleared through graded series of ethanol. Endogenous peroxidase will be quenched by incubation in 50% methanol/H₂O₂ and after rinsing with tap water; all sections will be pretreated for 30 minutes with 50 mmol/L EDTA using a steamer and cooled for additional 5 minutes.

All staining will be done automatically on DAKO Autostainer using the following antibodies to CD11c (Leica Microsystems 5D11), CD14 (Cell Marque EPR 3653), CD163 (DAKO 1F8), CD68 (DAKO PG-M1), CXCL13 (R&D Systems 53610), FOXP3 (Abcam 236AE/7), CD3 (R&D Systems), PD-L1 (405.9A11), PD-L2 (366C.9E5) and PD-1 (Abcam NAT). The sections will be viewed with an Olympus BXFA51 microscope and pictures taken with an Olympus DP71 camera.

17.42 **Fluorescence in situ hybridization (FISH):** FISH will be performed on Hodgkin lymphoma tissue sections to assess copy number on chromosome 9p24.1. The bacterial artificial chromosome probes (CHORI; www.chori.org) RP11-599H2O, which maps to 9p24.1 and includes *CD274* (encoding PD-L1, labeled with Spectrum Orange), and RP11-635N21, which also maps to 9p24.1 and includes *PDCD1LG2* (encoding PD-L2, labeled with Spectrum Green), will be cohybridized. A control centromeric probe, Spectrum Aqua-labeled *CEP9* (Abbott Molecular) that maps to 9p11-q11, will be hybridized according to the manufacturer's recommendations. Malignant Reed–Sternberg cells will be identified by means of nuclear morphologic features, and all such cells will be analyzed. Nuclei with a target:control probe ratio of at least 3:1 will be classified as amplified, those with a probe ratio of more than 1:1 but less than 3:1 will be classified as relative copy gain, and those with a probe ratio of 1:1 but with more than two copies of each probe will be classified as polysomic for chromosome 9p.

17.43 **Molecular Signature:** We will define the intratumoral molecular signature predictive of response to therapy in patients with Hodgkin lymphoma. We will use a previously described gene expression profile and optimize it for use in paraffin-embedded tissue [Sriedl et al]. The coefficients and the capture-based hybridization pipeline designed for formalin-fixed, paraffin-embedded tissues (FFPET) will be used. The genes include *CSFR1*, *PD-L1*, *PD-L2*, *EZH2*, *MEF2B*, *ARID1A*, *CARD11*, *FOXO1*, *CREBBP* and *EP300*. In addition, gene signatures downstream of specific mutations will be explored using a paraffin-based approach that follows gene set enrichment analysis of mutated cases. The signature(s) will be used to explore their ability to select cases with inferior outcomes.

19.0 Budget

- 19.1 Each site should review the test schedule (Section 4.0), taking into account local and regional coverage policies, to determine which items are standard of care and which are research at their site. Refer to the payment synopsis for funding provided per accrual for covering study costs, as well as any additional invoiceables that may be allowed.
- 19.2 Brentuximab vedotin and Nivolumab will be provided by Seattle Genetics and Bristol-Myers Squibb respectively, at no charge.
- 19.3 Tests to be research funded:
 - 19.31 Mandatory blood and tissue samples for research.

[Redacted]

[Redacted]

[Redacted]

[Redacted]

[Redacted]

[Redacted]

[Redacted]

[Redacted]

[Redacted]

[Redacted]

[Redacted]

[Redacted]

[Redacted]

[Redacted]

[Redacted]

[Redacted]

[Redacted]

[Redacted]

[Redacted]

[Redacted]

[Redacted]
